4.6. Dosage and Administration of Study Treatment(s)

See Section 5.1 for the dosage and administration of GSK2879552 and ATRA.

4.6.1. Meals and Dietary Restrictions

Subject should refrain from consumption of Seville oranges, grapefruit, grapefruit hybrids, grapefruit juice, pomelos, or exotic citrus fruits, which may inhibit efflux transporters, from 1 day prior to the first dose of study treatment(s) until the last dose of study drug.

GSK2879552 will be administered under fasting conditions, either 1 hour before or 2 hours after a meal. Subjects should take their morning ATRA dose fasted, at the same time as GSK2879552. If ATRA concentrations are lower than anticipated following fasted administration, subjects may be asked to take their morning ATRA dose with food. Subject should take their evening ATRA dose with food.

On serial PK sampling days, subjects should fast overnight (i.e., at least 8 hours) and should continue fasting until at least 2 hours after administration of the study medication.

Fasting will consist of avoiding the oral ingestion of calorie-containing products; however, ingestion of water is permitted. Any ongoing, usual concomitant medications may be administered while fasting.

4.6.2. Blinding

This is an open-label study.

4.7. Safety Management Guidelines

4.7.1. Liver Chemistry Stopping Criteria

Liver chemistry threshold stopping criteria have been designed to assure subject safety and to evaluate liver event etiology during administration of study treatment(s) and the follow-up period. Study treatment(s) will be stopped if any of the following liver chemistry stopping criteria is/are met:

1. Alanine aminotransferase (ALT) ≥ 5 X (times) upper limit of normal (ULN) and bilirubin ≥ 2 Xs ULN (or ALT ≥ 5 X ULN and international normalization ratio [INR] > 1.5)

NOTE: Serum bilirubin fractionation should be performed if testing is available. If fractionation is unavailable, urinary bilirubin is to be measured via dipstick (a measurement of direct bilirubin, which would suggest liver injury).

2. ALT ≥ 8 X ULN.
3. ALT ≥ 5 X ULN if associated with the appearance or worsening of rash or hepatitis symptoms (fatigue, nausea, vomiting, right upper quadrant pain or tenderness, or jaundice) or hypersensitivity (such as fever, rash or eosinophilia).
4. ALT ≥ 5 X ULN persists for ≥ 4 weeks.
5. ALT ≥ 5 X ULN and cannot be monitored weekly for 4 weeks.

Subjects with ALT ≥ 5 X ULN **and** < 8 Xs ULN **and** bilirubin < 2 X ULN, who do not exhibit hepatitis symptoms or rash, can continue study treatment(s) as long as they can be monitored weekly for 4 weeks. See following section for details on weekly follow-up procedures for these subjects.

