4.7.1.1. Liver Chemistry Follow-up Procedures

Refer to the diagram in [Appendix 5](#) for a visual presentation of the procedures listed below.

The procedures listed below are to be followed if a subject meets the liver chemistry stopping criteria defined in Section [4.7.1](#):

- Immediately withdraw the subject from study treatment.

- Notify the GSK Medical Monitor within 24 hours of learning of the abnormality to confirm the subject's study treatment(s) cessation and follow-up.
- Complete the "Safety Follow-Up Procedures" listed below.
- Complete the liver event electronic case report forms (eCRFs). If the event also meets the criteria of a serious adverse event (SAE) (see Section 8.2), the SAE data collection tool will be completed separately with the relevant details.
- Restart or rechallenge of study treatment requires approval as described in Section 9.

Safety Follow-Up Procedures for subjects with ALT ≥ 3 times ULN:

- Monitor subjects **weekly** until liver chemistries (ALT, aspartate aminotransferase [AST], alkaline phosphatase [ALP], and bilirubin) resolve, stabilize or return to within baseline values.

Safety Follow-Up Procedures for subjects with ALT ≥ 5 times ULN and bilirubin ≥ 2 times ULN (or ALT ≥ 5 times ULN and INR > 1.5):

- **This event is considered an SAE** (see Section 8.2). Serum bilirubin fractionation should be performed if testing is available. If fractionation is unavailable, urinary bilirubin is to be measured via dipstick (a measurement of direct bilirubin, which would suggest liver injury).
- Make every reasonable attempt to have subjects return to the clinic within 24 hours for repeat liver chemistries, additional testing, and close monitoring (with specialist or hepatology consultation recommended).
- Monitor subjects **twice weekly** until liver chemistries (ALT, AST, alkaline phosphatase, bilirubin) resolve, stabilize or return to within baseline values.

In addition, for all subjects with ALT ≥ 5 times ULN, every attempt must be made to also obtain the following:

- Viral hepatitis serology including:
 - Hepatitis A Immunoglobulin M (IgM) antibody.
 - Hepatitis B surface antigen and Hepatitis B Core Antibody (IgM).
 - Hepatitis C ribonucleic acid (RNA).
 - Cytomegalovirus IgM antibody.
 - Epstein-Barr viral capsid antigen IgM antibody (or if unavailable, obtain heterophile antibody or monospot testing).

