 - Hepatitis E IgM antibody (if subject resides outside the United States (US) or Canada, or has traveled outside US or Canada in past 3 months).
- Blood sample for PK analysis, obtained within 120 hours of last dose. Record the date/time of the PK blood sample draw and the date/time of the last dose of study treatment(s) prior to blood sample draw on the eCRF. If the date or time of the last dose is unclear, provide the subject's best approximation. If the date/time of the last

dose cannot be approximated OR a PK sample cannot be collected in the time period indicated above, **do not obtain a PK sample**. Instructions for sample handling and shipping are included in the SPM.

- Serum creatine phosphokinase and lactate dehydrogenase.
- Fractionate bilirubin, if total bilirubin ≥ 2 times ULN.
- Obtain complete blood count with differential to assess eosinophilia
- Record the appearance or worsening of clinical symptoms of hepatitis or hypersensitivity, such as fatigue, nausea, vomiting, right upper quadrant pain or tenderness, fever, rash or eosinophilia, on the AE eCRF.
- Record use of concomitant medication(s), acetaminophen, herbal remedies, other over-the-counter medication(s), or putative hepatotoxins on the Concomitant Medications eCRF.
- Record alcohol use on the Liver Events eCRF.

The following are required for subjects with ALT ≥ 5 times ULN **and** bilirubin ≥ 2 times ULN (>35% direct) or ALT ≥ 5 X ULN and INR > 1.5 but are optional for other abnormal liver chemistries:

- Anti-nuclear antibody, anti-smooth muscle antibody, and Type 1 anti-liver kidney microsomal antibodies.
- Liver imaging (ultrasound, magnetic resonance imaging [MRI] or computed tomography [CT] scan) to evaluate liver disease.
- Liver Imaging and/or Liver Biopsy eCRFs are also to be completed if these tests are performed.
- Serum acetaminophen adduct HPLC assay (quantifies potential acetaminophen contribution to liver injury in subjects with definite or likely acetaminophen use in the preceding week [James, 2009]). **NOTE: not required in China**
- Only in those with underlying chronic hepatitis B at study entry (identified by positive hepatitis B surface antigen): quantitative hepatitis B DNA and hepatitis delta antibody. . **NOTE:** if hepatitis delta antibody assay cannot be performed, it can be replaced with a PCR of hepatitis D RNA virus (where needed) – as outlined in: <http://www.ncbi.nlm.nih.gov/pmc/articles/PMC1153793>.

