4.8.4.2. Liver Function Test Elevation

If ALT \geq 5 X ULN, ATRA dose should be held while GSK2879552 dosing continues

- If resolved in 14 days, ATRA dose should resume at full dose
- If not resolved in 14 days, GSK2879552 dose should be also held.
 - If resolved in another 14 days, resume GSK2879552 at a reduced dose by minimum 25% and ATRA at full dose
 - If not resolved in another 14 days, withdraw the subject from the study.

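### Protocol 4.7.1's continuation paragraph, and 4.8.4.2 in the ATRA arm, read literally permit dosing that the liver stopping criteria forbid; non-rash hypersensitivity alone also has its Liver Event eCRF waived

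*Protocol*

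**What the plan says.** **Stops.** Protocol Section 4.7.1 makes stopping mandatory when any of five criteria is met. Criterion 1 includes ALT at or above 5 times ULN with INR above 1.5, whatever the bilirubin. Criterion 2 is ALT at or above 8 times ULN. Criterion 3 is ALT at or above 5 times ULN associated with rash, with hepatitis symptoms (fatigue, nausea, vomiting, right-upper-quadrant pain, jaundice), "or hypersensitivity (such as fever, rash or eosinophilia".

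**Continuation.** The next paragraph covers ALT from 5 to below 8 times ULN with bilirubin below 2 times ULN. It says that subjects "who do not exhibit hepatitis symptoms or rash, can continue study treatment(s) as long as they can be monitored weekly for 4 weeks".

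**Procedures.** Section 4.7.1.1 applies to every subject who meets a stopping criterion. It calls for immediate withdrawal from treatment and a liver event form: "Complete the liver event electronic case report forms (eCRFs"). For the bilirubin or INR combination it adds: "This event is considered an SAE".

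**Reporting.** Section 8.5.2 has three liver rows.
- Row 1 covers ALT at or above 5 times ULN with raised bilirubin, or with INR above 1.5 if measured. It requires the SAE tool and the Liver Event eCRF.
- Row 2 covers ALT at or above 8 times ULN, ALT at or above 5 times ULN with hepatitis or rash, and persistence for 4 weeks. It requires the eCRF.
- Row 3 covers ALT from 5 to below 8 times ULN with bilirubin below 2 times ULN. It waives the eCRF unless the elevation lasts 4 weeks or weekly monitoring is impossible.

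**ATRA arm.** Section 4.8.4.2 says that at ALT at or above 5 times ULN, "ATRA dose should be held while GSK2879552 dosing continues". GSK2879552 is held as well only if the elevation has not resolved after 14 days. Section 1.4.5.1 says that both the stopping criteria and this guideline exist, but not which one governs.

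**The concern.** A permissive rule and a mandatory rule in the same section give different answers for the same subject. The continuation paragraph names hepatitis symptoms and rash but not INR or the other hypersensitivity signs, and rows 2 and 3 of 8.5.2 repeat the hypersensitivity omission. A site checking 4.7.1 against 8.5.2 would find the permissive reading supported.

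The omitted sign matters by the protocol's own account. Section 9.1 lists hypersensitivity at the initial liver injury among the risk factors for a fatal rechallenge, and Section 9.2 requires it to be excluded before a restart. Attribution is also difficult in this population: febrile neutropenia was the most common SAE (Section 1.3.5), and fever is reported in 83% of patients in the cited ATRA labelling (Section 1.3.6.1).

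In the ATRA arm, Section 1.4.5.1 expects raised liver tests in 50% to 60% of patients, so a rule for ALT at or above 5 times ULN may well be needed.

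**Working it through.** The plan states no figure to reproduce. This is a check of whether the rules agree.

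**Setting.** ALT from 5 to below 8 times ULN, bilirubin below 2 times ULN, weekly monitoring possible, duration under 4 weeks. Criteria 2, 4 and 5 and the bilirubin part of criterion 1 are therefore not met. Let I = INR above 1.5, S = hepatitis symptoms or rash, and H = non-rash hypersensitivity associated with the ALT rise.

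**Rules.** Stop = I or S or H (criteria 1 and 3). Continuation allowed = not S. Row 1 of 8.5.2 = I; row 2 = S; row 3 = every combination in this band.

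| Combination | Must stop | Paragraph allows dosing | Liver rows matched |
|---|---|---|---|
| none | no | yes | 3 |
| H | yes | yes (conflict) | 3 only |
| S | yes | no | 2, 3 |
| S, H | yes | no | 2, 3 |
| I | yes | yes (conflict) | 1, 3 |
| I, H | yes | yes (conflict) | 1, 3 |
| I, S | yes | no | 1, 2, 3 |
| I, S, H | yes | no | 1, 2, 3 |

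**INR measured.** There are 2 × 2 × 2 = 8 combinations. Stop applies in 7, continuation is allowed in 4, and both hold in 3. Of those 3, the 2 with INR above 1.5 fall under row 1 and SAE handling. Of the 7 stop combinations, 6 match row 1 or row 2, so 7 − 6 = 1 (H alone) matches row 3 only. That is the case where 4.7.1.1 requires the form and 8.5.2 waives it.

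**INR not measured** (footnote c of 8.5.2 does not require it). There are 2 × 2 = 4 combinations. Stop applies in 3, continuation is allowed in 2, and both hold in 1, which is again H alone.

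**ATRA arm, same band, INR measured.** Section 4.8.4.2 read literally continues GSK2879552 at first in 8 of 8 combinations, and 7 of those meet a 4.7.1 stop. In the remaining one, 4.7.1 lets study treatment continue while 4.8.4.2 holds ATRA. That is not a contradiction, because the first rule is permissive and the second is more specific.

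**ATRA arm, above the band.** Section 4.8.4.2 has no upper ALT limit. At ALT at or above 8 times ULN, criterion 2 alone requires a stop while 4.8.4.2 says GSK2879552 goes on. Its resumption steps do not mention the approval that Section 9 requires after a liver stop.

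**After the fix.** Adding INR at or below 1.5 (if measured) and no hypersensitivity to the continuation paragraph reduces the 3 conflicts to 0. Adding hypersensitivity to row 2, and limiting row 3 to subjects who meet no stop, reduces the form gap from 1 to 0.

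**The case against.** The strongest reply is that the stopping list already controls. It is mandatory, whereas the continuation paragraph only permits. Section 4.7.1.1 orders immediate withdrawal, Section 6.3 ends treatment when the 4.7.1 criteria are met, and Section 9 bars restart without approval. This stands: all four point the same way, although none is an explicit tie-break.

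A second reply is that hepatitis symptoms or rash is shorthand for the whole of criterion 3, since 4.7.1.1 elsewhere groups hepatitis and hypersensitivity signs together. This is plausible as intent, but criterion 3 itself lists rash, hepatitis symptoms and hypersensitivity separately.

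A third reply is that the Appendix 5 diagram may settle the order. It could not be seen here, although its footnote shows that it includes INR. That limit is accepted.

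The remaining case is also narrow, and it is not unmonitored. Row 3 keeps notification within 24 hours, and 4.7.1.1 puts hypersensitivity signs on the AE eCRF. Judging whether a fever is associated with the ALT rise comes from criterion 3 and would remain after any rewording.

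On ATRA, the 14 + 14 = 28 days before withdrawal in 4.8.4.2 matches the 4-week limit of criterion 4, which suggests the rule was meant to work inside 4.7.1. That is a fair reading of intent, but it does not supply the missing exception for ALT at or above 8 times ULN.

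A reader might infer that subjects were dosed through a mandatory stop, that the INR case is unprotected, or that 3 of 8 and 7 of 8 are proportions of subjects. The documents support none of these. They report no such subjects, the INR case is an SAE with its form required, and the counts are unweighted logical combinations.

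**Conclusion.** The inconsistency is real and lies in current protocol text, but it is of low severity. Read literally, the continuation paragraph conflicts with the stops in 3 of 8 combinations. With the mandatory list most likely prevailing and the INR combinations covered, what remains is one case, non-rash hypersensitivity alone, with contradictory instructions on the Liver Event eCRF. The ATRA rule lacks an exception for the 4.7.1 stops, including ALT at or above 8 times ULN, and does not refer to Section 9.

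How often either situation arose cannot be judged from the documents. It would go too far to say that safety results are biased. No effect on SAE counts is shown. Nor is one shown on the SAP's Hy's law summary (SAP 7.3.1), which is defined by laboratory values rather than by the form. An effect on SAP Listing 45 is possible if that listing draws on the Liver Event eCRF, but the SAP does not state its source. The conclusion assumes that the Appendix 5 diagram contains no precedence rule; if it does, the point weakens further.

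**What to change.** In the protocol wording:
- Limit the continuation paragraph in 4.7.1 and row 3 of 8.5.2 to subjects who meet none of criteria 1 to 5 (INR at or below 1.5 if measured, and no hypersensitivity signs associated with the ALT rise).
- Add hypersensitivity to row 2 of 8.5.2.
- State that the 4.7.1 stops and Section 9 restart approval take precedence over 4.8.4.2, and that ATRA is still held when the continuation paragraph applies.

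These changes add no assessments. INR stays conditional on measurement, and 4.7.1.1 already asks for a differential count at ALT at or above 5 times ULN.

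Because the study ended early (SAP 2.1), the step that still applies is to check records with ALT at or above 5 times ULN, including ALT at or above 8 times ULN in the ATRA arm, against criteria 1 to 5 before Listing 45 is produced. The cost is one review of laboratory and AE data already held.

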4.7.1.1. Liver Chemistry Follow-up Procedures

Refer to the diagram in [Appendix 5](#) for a visual presentation of the procedures listed below.

The procedures listed below are to be followed if a subject meets the liver chemistry stopping criteria defined in Section [4.7.1](#):

- Immediately withdraw the subject from study treatment.

- Notify the GSK Medical Monitor within 24 hours of learning of the abnormality to confirm the subject's study treatment(s) cessation and follow-up.
- Complete the "Safety Follow-Up Procedures" listed below.
- Complete the liver event electronic case report forms (eCRFs). If the event also meets the criteria of a serious adverse event (SAE) (see Section 8.2), the SAE data collection tool will be completed separately with the relevant details.
- Restart or rechallenge of study treatment requires approval as described in Section 9.

Safety Follow-Up Procedures for subjects with ALT ≥ 3 times ULN:

- Monitor subjects **weekly** until liver chemistries (ALT, aspartate aminotransferase [AST], alkaline phosphatase [ALP], and bilirubin) resolve, stabilize or return to within baseline values.

Safety Follow-Up Procedures for subjects with ALT ≥ 5 times ULN and bilirubin ≥ 2 times ULN (or ALT ≥ 5 times ULN and INR > 1.5):

- **This event is considered an SAE** (see Section 8.2). Serum bilirubin fractionation should be performed if testing is available. If fractionation is unavailable, urinary bilirubin is to be measured via dipstick (a measurement of direct bilirubin, which would suggest liver injury).
- Make every reasonable attempt to have subjects return to the clinic within 24 hours for repeat liver chemistries, additional testing, and close monitoring (with specialist or hepatology consultation recommended).
- Monitor subjects **twice weekly** until liver chemistries (ALT, AST, alkaline phosphatase, bilirubin) resolve, stabilize or return to within baseline values.

In addition, for all subjects with ALT ≥ 5 times ULN, every attempt must be made to also obtain the following:

- Viral hepatitis serology including:
 - Hepatitis A Immunoglobulin M (IgM) antibody.
 - Hepatitis B surface antigen and Hepatitis B Core Antibody (IgM).
 - Hepatitis C ribonucleic acid (RNA).
 - Cytomegalovirus IgM antibody.
 - Epstein-Barr viral capsid antigen IgM antibody (or if unavailable, obtain heterophile antibody or monospot testing).
 - Hepatitis E IgM antibody (if subject resides outside the United States (US) or Canada, or has traveled outside US or Canada in past 3 months).
- Blood sample for PK analysis, obtained within 120 hours of last dose. Record the date/time of the PK blood sample draw and the date/time of the last dose of study treatment(s) prior to blood sample draw on the eCRF. If the date or time of the last dose is unclear, provide the subject's best approximation. If the date/time of the last

dose cannot be approximated OR a PK sample cannot be collected in the time period indicated above, **do not obtain a PK sample**. Instructions for sample handling and shipping are included in the SPM.

- Serum creatine phosphokinase and lactate dehydrogenase.
- Fractionate bilirubin, if total bilirubin ≥ 2 times ULN.
- Obtain complete blood count with differential to assess eosinophilia
- Record the appearance or worsening of clinical symptoms of hepatitis or hypersensitivity, such as fatigue, nausea, vomiting, right upper quadrant pain or tenderness, fever, rash or eosinophilia, on the AE eCRF.
- Record use of concomitant medication(s), acetaminophen, herbal remedies, other over-the-counter medication(s), or putative hepatotoxins on the Concomitant Medications eCRF.
- Record alcohol use on the Liver Events eCRF.

The following are required for subjects with ALT ≥ 5 times ULN **and** bilirubin ≥ 2 times ULN (>35% direct) or ALT ≥ 5 X ULN and INR > 1.5 but are optional for other abnormal liver chemistries:

- Anti-nuclear antibody, anti-smooth muscle antibody, and Type 1 anti-liver kidney microsomal antibodies.
- Liver imaging (ultrasound, magnetic resonance imaging [MRI] or computed tomography [CT] scan) to evaluate liver disease.
- Liver Imaging and/or Liver Biopsy eCRFs are also to be completed if these tests are performed.
- Serum acetaminophen adduct HPLC assay (quantifies potential acetaminophen contribution to liver injury in subjects with definite or likely acetaminophen use in the preceding week [James, 2009]). **NOTE: not required in China**
- Only in those with underlying chronic hepatitis B at study entry (identified by positive hepatitis B surface antigen): quantitative hepatitis B DNA and hepatitis delta antibody. . **NOTE:** if hepatitis delta antibody assay cannot be performed, it can be replaced with a PCR of hepatitis D RNA virus (where needed) – as outlined in: <http://www.ncbi.nlm.nih.gov/pmc/articles/PMC1153793>.

4.7.2. QTc Stopping Criteria

If a subject that meets the corrected QT (QTc)¹ interval duration criteria below, study treatment(s) will be withheld.

- QT interval corrected for heart rate by Fridericia's formula ($QTcF = QT / \text{CubeRootRR}$) >500 msec
- Increase of QTcF by ≥ 60 msec from baseline
- For patients with underlying **bundle branch block**, follow the discontinuation criteria listed below:

Baseline QTc with Bundle Branch Block	Discontinuation QTc with Bundle Branch Block
< 450 msec	> 500 msec
450 – 480 msec	≥ 530 msec

1Based on average QTc value of triplicate electrocardiograms (ECGs) to include manual over-read. For example, if an ECG demonstrates a prolonged QT interval, obtain 2 additional ECGs over a brief period (e.g., within approximately 10 minutes of the abnormal ECG, if possible, and approximately 10 minutes apart from each other), and then use the averaged QTc values of the 3 ECGs to determine whether the subjects should have study treatment(s) withheld.

If the QTc prolongation resolves to Grade 1 or baseline, the subject may be re-started on the study treatment(s) if the investigator and GSK Medical Monitor agree that the subject will benefit from further treatment.

For subjects recruited in France, please refer to [Appendix 7](#) for the French specific QTc stopping criteria.

4.7.3. Mental Status Stopping Criteria

Enrollment will be stopped upon the occurrence of any encephalopathy, unless clearly attributable to central nervous system disease involvement or intercurrent illness.

Study treatment will be held and neurology consult obtained if any of the 3 criteria below are met:

- A decrease of 3 points or more from baseline (Pre-dose Day 1) MOCA score
- Any MOCA score of <22
- Any other indication of early encephalopathy as determined by patient history or physical exam

The treatment may resume if one of the following criteria is met:

- A reversible cause other than study treatment is identified and both MOCA score and symptoms return to baseline or to the MOCA score before the decrease.
- Evaluated by a neurologist and found to have no clear signs/symptoms of encephalopathy or other cognitive dysfunction. This is applicable only in the absence of decrease in MOCA score.

All treatment restarts must be approved by GSK medical monitor.

The treatment should be permanently discontinued for subjects with documented symptoms with no other cause, even if they return to baseline.

